5.5 Secondary endpoints

Secondary endpoints to be measured during the two treatment phases will include, but not be limited to the following:

Virologic measures of interest

- Proportion of participants in each treatment group with plasma HIV-1 RNA <50 copies/mL at week 12 and week 18

Immunologic measures of interest

- Differences between treatment groups in mean change from baseline in CD4+ cell counts at week 12
- Differences between treatment groups in mean change from baseline in CD4+ cell counts at week 18
- Differences between treatment groups in mean change from baseline in CD8+ cell counts at week 12
- Differences between treatment groups in mean change from baseline in CD8+ cell counts at week 18

Activation/Coagulation measures of interest

- Percentage of patients in each treatment group with d-dimer <165ng/mL (0.165mg/L) at week 8 and week 12
- Percentage of patients in each treatment group with d-dimer >165ng/mL (0.165mg/L) at week 18
- Differences between treatment groups in mean change from baseline log₁₀ d-dimer at week 18
- Differences between treatment groups in mean change from baseline log₁₀ hs-CRP at week 8 and week 12
- Differences between treatment groups in mean change from baseline log₁₀ hs-CRP at week 18
- Differences between treatment groups in mean change from baseline log₁₀ IL-6 at week 8 and week 12
- Differences between treatment groups in mean change from baseline log₁₀ IL-6 at week 18

Safety endpoints

- Total number of participants in each treatment group with Type 1, 2, 3, 4 or 5 bleeding episodes (using BARC¹⁶ criteria – see Appendix 2)
- Total number of participants in each treatment group with any Serious Adverse Event (SAE) and the cumulative incidence of SAEs.
- Total number of participants in each treatment group with any Adverse event (AE) and the cumulative incidence of AEs
- Changes from baseline in selected serum biochemical parameters, including changes in renal function measured by the CKD-EPI estimate of creatinine clearance

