6.2 Analysis Plan

6.2.1 Statistical analysis

Baseline characteristics will be summarised by randomised group. Patients failing to complete study drug will be listed, with accompanying reasons. The primary endpoint will be mean changes in log₁₀ d-dimer levels from baseline at weeks 8 and 12. The proportion of patients with d-dimer < 165 ng/mL will also be summarised.

Mean or median changes, or percentages, as appropriate, in primary and secondary endpoints will be plotted by study week.

Formal analyses will compare the randomised treatment arms in terms of mean differences in changes in log₁₀ d-dimer at week 8 and week 12 using repeated measures regression methods. Models will be fitted using maximum likelihood methods using robust standard errors. Simple unadjusted models will initially be used to estimate the difference between randomised treatment arms in mean changes in log₁₀ d-dimer. Models adjusted for key baseline covariates will also be fitted. If there is overall evidence of a difference between randomised treatment arms at $2p < 0.05$, then further sensitivity analyses will also be performed using simple two-sample (t-test or rank-sum test) applied to the mean change in log₁₀ d-dimer at weeks 8 and 12.

Similar longitudinal methods will also be used to analyse mean changes from baseline in, or proportions of, secondary endpoints at weeks 8 and 12.

Differences between randomised treatment arms in mean changes in, or proportions of, all endpoints at week 18 will be investigated using linear regression or logistic regression methods.

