11.0 Adverse Event Recording & Reporting

11.1 Adverse Events

The definition of an adverse event is any untoward medical occurrence in a participant administered with a pharmaceutical product which does not necessarily have a causal relationship with the product. Where adverse events are related to the drug, they may be referred to as Adverse Drug Reactions.

Adverse events and adverse drug reactions may occur in the course of this study and within the specified follow-up period. These events may also occur in screened participants during the screening period prior to

randomisation as a result of protocol-specified interventions. All such events will be recorded at each study visit on the adverse event case report form.

In this study we will be collecting all grade (grade 1-4) clinical adverse events. As a general rule, isolated laboratory abnormalities in the absence of clinical symptoms and/or signs should not be captured as adverse events. If the laboratory event becomes clinically significant, then the resulting clinical event should be reported as an adverse event (e.g. low haemoglobin should be reported as anaemia).

Pre-existing conditions or diseases that occur during the study (e.g. seasonal allergies, asthma or recurrent headaches) should not be considered as adverse events unless they change in frequency or severity. In this study we will be collecting all grade (grade 1-4) clinical adverse events. If known, the diagnosis of the underlying illness or disorder should be recorded, rather than its individual symptoms.

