Creatinine Clearance¹⁵ or eGFR, Low Report only one	NA	< 90 to 60 ml/min or ml/min/1.73 m ² OR 10 to < 30% decrease from baseline	< 60 to 30 ml/min or ml/min/1.73 m ² OR ≥ 30 to < 50% decrease from baseline	< 30 ml/min or ml/min/1.73 m ² OR ≥ 50% decrease from baseline or dialysis needed
Glucose (mg/dL; mmol/L) Fasting, High	110 to 125 6.11 to < 6.95	> 125 to 250 6.95 to < 13.89	> 250 to 500 13.89 to < 27.75	> 500 ≥ 27.75
Nonfasting, High	116 to 160 6.44 to < 8.89	> 160 to 250 8.89 to < 13.89	> 250 to 500 13.89 to < 27.75	> 500 ≥ 27.75
Glucose, Low (mg/dL; mmol/L) ≥ 1 month of age	55 to 64 3.05 to 3.55	40 to < 55 2.22 to < 3.05	30 to < 40 1.67 to < 2.22	< 30 < 1.67
< 1 month of age	50 to 54 2.78 to 3.00	40 to < 50 2.22 to < 2.78	30 to < 40 1.67 to < 2.22	< 30 < 1.67
Lactate, High	ULN to < 2.0 x ULN without acidosis	≥ 2.0 x ULN without acidosis	Increased lactate with pH < 7.3 without life- threatening consequences	Increased lactate with pH < 7.3 with life- threatening consequences

¹⁵ Use the applicable formula (i.e., Cockcroft-Gault in mL/min or Schwartz in mL/min/1.73m²).

Chemistries

PARAMETER	GRADE 1 MILD	GRADE 2 MODERATE	GRADE 3 SEVERE	GRADE 4 POTENTIALLY LIFE- THREATENING
Lipase, High	1.1 to < 1.5 x ULN	1.5 to < 3.0 x ULN	3.0 to < 5.0 x ULN	≥ 5.0 x ULN
Lipid Disorders (mg/dL; mmol/L)				
Cholesterol, Fasting, High ≥ 18 years of age	200 to < 240 5.18 to < 6.19	240 to < 300 6.19 to < 7.77	≥ 300 ≥ 7.77	NA
< 18 years of age	170 to < 200 4.40 to < 5.15	200 to < 300 5.15 to < 7.77	≥ 300 ≥ 7.77	NA
LDL, Fasting, High ≥ 18 years of age	130 to < 160 3.37 to < 4.12	160 to < 190 4.12 to < 4.90	≥ 190 ≥ 4.90	NA
> 2 to < 18 years of age	110 to < 130 2.85 to < 3.34	130 to < 190 3.34 to < 4.90	≥ 190 ≥ 4.90	NA
Triglycerides, Fasting, High	150 to 300 1.71 to 3.42	>300 to 500 >3.42 to 5.7	>500 to < 1,000 >5.7 to 11.4	> 1,000 > 11.4
Magnesium¹⁶, Low (mEq/L; mmol/L)	1.2 to < 1.4 0.60 to < 0.70	0.9 to < 1.2 0.45 to < 0.60	0.6 to < 0.9 0.30 to < 0.45	< 0.6 < 0.30
Phosphate, Low (mg/dL; mmol/L)				
> 14 years of age	2.0 to < LLN 0.81 to < LLN	1.4 to < 2.0 0.65 to < 0.81	1.0 to < 1.4 0.32 to < 0.65	< 1.0 < 0.32
1 to 14 years of age	3.0 to < 3.5 0.97 to < 1.13	2.5 to < 3.0 0.81 to < 0.97	1.5 to < 2.5 0.48 to < 0.81	< 1.5 < 0.48
< 1 year of age	3.5 to < 4.5 1.13 to < 1.45	2.5 to < 3.5 0.81 to < 1.13	1.5 to < 2.5 0.48 to < 0.81	< 1.5 < 0.48
Potassium, High (mEq/L; mmol/L)	5.6 to < 6.0 5.6 to < 6.0	6.0 to < 6.5 6.0 to < 6.5	6.5 to < 7.0 6.5 to < 7.0	≥ 7.0 ≥ 7.0

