4.3 Statistical analysis

All efficacy endpoints will be summarised by randomised treatment and study visit. Continuous measures will be summarised as means and standard deviations, categorical measures as n and percent.

Formal statistical comparisons between randomised treatment arms will use repeated measures regression methods as appropriate to continuous and binary data. Precise models to be used will depend on data and fit to model assumptions, but *a priori* choice will be generalised estimating equations with robust standard errors. Initial analyses will be unadjusted comparison of randomised treatments with baseline value only as a covariate, but further adjusted analyses may be performed as needed.

Further regression modelling may be performed to explore how primary and secondary activation and coagulation endpoints evolve over time.

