5.2 Adverse Events

Bleeding adverse events

Total number of participants with Type 1, 2, 3, 4 or 5 bleeding episodes using BARC criteria. Bleeding episodes will be summarised by type and randomised treatment.

Serious Adverse Events

Total number of participants with any Serious Adverse Event (SAE) and the cumulative incidence of SAEs. SAEs will be summarised by randomised treatment and relationship to study drug.

Adverse events

Total number of participants with any Adverse event (AE) and the cumulative incidence of AEs. All AEs, and grade 3 or 4 AEs, will be summarised by MedDRA group term, relationship to study drug and randomised treatment.

Laboratory adverse events

Total number of participants with laboratory or biochemical adverse events, according to DAIDS criteria, in particular renal function measured by the CKD-EPI estimate of creatinine clearance. Laboratory AEs will be summarised by grade and randomised treatment.

Statistical analysis of adverse event data

The proportion of patients with adverse events will be compared between randomised treatments using chi-square tests, Fisher's exact test or similar as appropriate to the data. Differences in proportions of patients with events by randomised treatments will be summarised as 95% confidence intervals.

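### The SAP, as supplied, replaces the protocol's safety endpoint of change from baseline in biochemistry and CKD-EPI renal function with DAIDS-graded counts, which are less sensitive and mix in baseline status

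*Protocol*

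**What the plan says.** Protocol 5.5 and the synopsis list four safety endpoints: bleeding by BARC type, SAEs, AEs, and "Changes from baseline in selected serum biochemical parameters, including changes in renal function measured by the CKD-EPI estimate of creatinine clearance".

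Protocol 6.2.2 (Safety analysis) gives no method for the fourth. Protocol 6.2.1 has a general sentence: "Differences between randomised treatment arms in mean changes in, or proportions of, all endpoints at week 18 will be investigated", by linear or logistic regression.

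SAP 5.2 takes up bleeding, SAEs and AEs in the protocol's order. In fourth place it has "Total number of participants with laboratory or biochemical adverse events, according to DAIDS criteria, in particular renal function measured by the CKD-EPI estimate". The summary planned for this count is short: "Laboratory AEs will be summarised by grade and randomised treatment". Event proportions "will be compared between randomised treatments using chi-square tests, Fisher's exact test or similar as appropriate to the data", with 95% confidence intervals for the differences.

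Means and standard deviations appear only in SAP 4.3, whose scope is limited: "All efficacy endpoints will be summarised by randomised treatment and study visit". SAP 4.2 lists no biochemistry.

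**The concern.** The protocol's measure is a change on a continuous scale. The SAP's is the number of people who cross a grade boundary. Followed as supplied, the SAP yields no mean change in eGFR, creatinine, transaminases or electrolytes, and no interval for a difference between arms in such a change. The CKD-EPI wording moves from one measure to the other, so this reads as a substitution and not merely as missing detail.

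Three features make the count a poor stand-in:

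- **Baseline status.** In the DAIDS chemistry table (Protocol Appendix 1), eGFR has no Grade 1, and any value below 90 is at least Grade 2. Exclusion criterion 5 applies only below 30. Participants can therefore be events before taking study drug, and the SAP does not say whether grades present at week 0 count.
- **Thresholds.** ALT and AST grades start at 1.25 x ULN and creatinine at 1.1 x ULN. Shifts that stay below these limits score nothing, apart from the creatinine grades defined by a rise above baseline.
- **Data source.** Protocol 11.1 says that, as a general rule, "isolated laboratory abnormalities in the absence of clinical symptoms and/or signs should not be captured as adverse events". If the SAP count draws on reported AEs and not on the laboratory data, symptom-free falls may not enter it.

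At stake is whether the report of a small trial gives an estimate, with its uncertainty, for a safety endpoint that its protocol named.

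**Working it through.** **The plan's own figure.** The only sample-size calculation is for the primary endpoint (Protocol 6.1): SD 0.4, correlation 0.5, 28 per arm. The SD of the mean of two visits is 0.4 x sqrt((1 + 0.5)/2) = 0.346. With power = Φ(d x sqrt(n/2) − 1.96):

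- d = 0.26/0.346 = 0.751: Φ(2.81 − 1.96) = 80%.
- d = 0.30/0.346 = 0.866: Φ(3.24 − 1.96) = 90%.

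Both stated figures reproduce. Nothing comparable is given for biochemistry.

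**Assumed inputs (not in the documents).** Baseline eGFR mean 85, 95 or 105 with SD 15; SD of change 8, 10 or 12 mL/min/1.73m²; one post-baseline visit; two-sided 5% test. Grades follow Appendix 1: Grade 2 for a value below 90 or a "10 to < 30% decrease from baseline", Grade 3 below 60 or a fall of 30% to under 50%, Grade 4 below 30 or a fall of at least 50%.

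**Continuous analysis by formula, one visit:**

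| True fall | 28 per arm | 30 per arm |
|---|---|---|
| 0.50 SD | 46% | 49% |
| 0.65 SD | 68% | 71% |
| 0.75 SD | 80% | 83% |
| 1.00 SD | 96% | 97% |

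**Simulated comparison, 28 per arm, 4,000 trials per setting, true fall 0.75 SD (6 to 9 units).** Ranges run over the assumed inputs.

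| Analysis | Chi-square | Fisher |
|---|---|---|
| Any Grade 2 or higher | 21–46% | 14–36% |
| Grade worse than baseline | 28–50% | 16–39% |
| Fall of at least 10% | 45–58% | 32–47% |

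The t-test on change has 78% to 80% in the same settings.

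**With 30 per arm and a true fall of 0.75 to 0.8 SD.** The baseline-adjusted comparison of change has about 81% to 86% power. The any-grade and worse-grade rules have 13% to 42% by Fisher and 20% to 52% by chi-square. A fall of at least 10% has 34% to 64%, depending on the test.

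**Other effect sizes, 28 per arm.**

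- 0.5 SD (5 units, SD 10): t-test 45% to 47%; counts 14% to 29% by chi-square and 9% to 20% by Fisher.
- 10 units (0.83 to 1.25 SD): t-test 86% to 99.6%; counts 38% to 94% by chi-square and 27% to 90% by Fisher, depending on the rule.

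**Baseline contamination.** At an assumed baseline mean of 85, the share already below 90 is Φ((90 − 85)/15) = Φ(0.33) = 63%. In the simulation about 62% of controls are Grade 2 or higher at follow-up with no drug effect.

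**Precision of the omitted analysis.** The 95% CI half-width is t(57) x SD x sqrt(2/30) = 2.00 x 0.258 x SD, which gives 4.1, 5.2 and 6.2 units for SD 8, 10 and 12.

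**The case against.** **The absence may not be real.** The supplied SAP breaks off mid-sentence in 2.1, has no section 3, and runs from 5 to 5.2. A paragraph on laboratory parameters could have stood in a 5.1. This stands as a caveat, and the sponsor can settle it at once. It does not change what 5.2 says, and 5.2 is where the CKD-EPI endpoint now sits.

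**Renal function is still covered.** A reader might infer that the SAP drops it. It does not: 5.2 names it and reports it by grade and arm, and the DAIDS eGFR and creatinine rows partly encode change from baseline. What is lost is the continuous change.

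**The protocol may already supply the analysis, or may never have promised a comparison.** If the week-18 sentence in Protocol 6.2.1 reaches safety endpoints, a regression at that visit is prespecified and the SAP does not revoke it. If it does not, 6.2.2 offers no formal test, and the endpoint lacks the between-group wording used for the continuous efficacy endpoints. Either reading is possible, so a formal comparison was not clearly required. A report of the change itself was.

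**Renal harm is not a flagged risk.** Protocol 8.1 gives faecal elimination as the main route, 10.2.4 requires no renal dose adjustment, and 10.3 lists no renal reaction. This makes a mean fall of 6 to 9 units hypothetical and keeps the point modest.

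**The power contrast depends on choices.** The eGFR inputs are assumed, the counting rule is unspecified, and one visit was simulated although the count may pool weeks 12 and 18. All of this stands, and is why ranges are shown.

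**Conclusion.** The mismatch between Protocol 5.5 and SAP 5.2 holds on the supplied text and needs no assumed figure. The graded count is also the less sensitive measure in every setting examined. At 0.75 to 0.8 SD, with 30 per arm, power falls from about 81% to 86% for change to 13% to 52% for the any-grade or worse-grade counts, and to 34% to 64% for a fall of at least 10%. These sizes rest on the assumed eGFR inputs.

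Two stronger conclusions are tempting and are not supported. One is that a moderate renal effect would usually be missed because of the SAP. Under the 10% rule with chi-square, detection at 0.75 SD is close to an even chance. At 10 units counts can reach 94%, and at 0.5 SD the continuous analysis itself has only about 45% to 47%, so trial size is also a limit. The other is that a hepatic signal would be missed: nothing in the documents or in the calculation above sizes that.

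This is a correction worth making to a secondary safety endpoint. It does not bear on the primary analysis.

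**What to change.** First confirm whether a SAP section 5.1 exists and covers this endpoint. If not, add to SAP 5.2:

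- Name the selected biochemical parameters, and summarise by arm their change from week 0 to week 12 and from week 0 to week 18.
- For CKD-EPI eGFR, give the between-arm difference with its 95% CI from a linear regression adjusted for the week-0 value. Do the same for ALT and AST on the log scale if they are among the selected parameters.
- Report other chemistries descriptively.
- Keep the graded counts as support, stating whether they come from the laboratory data or from reported AEs and whether grades present at week 0 count.

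The cost is a few lines and one table, because biochemistry is already collected at weeks 0, 12 and 18. The downside is a few extra safety comparisons without multiplicity control: two for eGFR, or six with ALT and AST (three parameters x two visits). They should be read through their confidence intervals. Testing every chemistry formally would instead mean 10 or 11 parameters x two visits, or 20 to 22 comparisons (the flow chart lists calcium, section 9.3.2 does not). At the 5% level about one would be expected to be a false positive, so the formal comparison should stay narrow.

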5.6 Exploratory endpoints

During conduct of the study blood will be collected to support a range of exploratory laboratory analyses. If the primary endpoint of the trial is reached, the following measures of interest will be analysed:

Virological measures

- Cell associated HIV RNA/DNA
- Ultrasensitive plasma viral load

Immunopathogenesis measures

- Plasma markers of monocyte activation (sCD14 and sCD163)
- Antibody function (ADCC)
- NK cell activation
- T cell activation markers (e.g. CD38+ HLA+DR+ expression on CD4+/CD8+ cells)
- PAR-1 expression (to be analysed on fresh whole blood collected from a subset of participants at participating sites with the capacity to perform this assay in real time)

6.0 Study design & Statistics

This is an international, multi-centre, double-blind, placebo controlled trial. Randomisation will be stratified by clinical site.

Consenting participants will be screened and within 14 days randomly allocated to receive either vorapaxar sulphate (2.5mg qd) or matched placebo once daily for 12 weeks (phase 1). At the week 12 visit, all study treatment will stop for 6 weeks (phase 2). Patients will be seen for a final visit at week 18.

The study designed is summarised in Figure 1.

[figure not shown]

Figure 1. Study Design

60 participants will be randomised from approximately 7 selected centres in Australia and the USA and followed for a total of 18 weeks. It is anticipated that approximately 120 patients will need to be screened to randomise 60 participants. It is expected that the majority of ineligible participants through screening will be those with low d-dimer levels.

6.1 Sample size determination

Assumptions are based on data from the STEAL trial¹⁴. Excluding patients with d-dimer < 200 ng/mL, the standard deviation in change in log₁₀ d-dimer is 0.356 at week 12 and 0.414 at week 24. The correlation of these two endpoints is 0.5726.

Using a repeated measures regression analysis at week 8 and 12, variability in change in log₁₀ d-dimer = 0.4, and correlation between these two time points as 0.5 (STEAL trial¹⁴), then a total sample size of 56 patients (2x28) gives 80% (90%) power to detect a mean difference of 0.26 (0.30) logs. A total of 60 patients gives some modest allowance for non-completion.

Mean baseline d-dimer in STEAL¹⁵ (excluding patients with d-dimer < 200 ng/mL at baseline) was 430 ng/mL. Mean log₁₀ decrease in STEAL was 0.07 logs, which corresponds to about a 15% decrease – i.e. in the control arm we might expect a decrease from 430 to about 370 ng/mL. We are powered to detect log differences of the order of 0.26, so in total in the vorapaxar arm we expect a 0.33 log decrease – i.e. a decrease from 430 to about 200 ng/mL. In absolute terms we have 80% power to detect a difference in d-dimer changes of around 170 ng/mL.

These are quite large effect sizes, both compared with the expected variability (0.75 standard deviations), and in absolute terms (differences in d-dimer changes of around 170 ng/mL from expected baseline mean of 430 ng/mL). However, we believe that such large effects would be clinically significant, and will be required to justify expanded studies of vorapaxar treatment in HIV-positive individuals.

6.2 Analysis Plan

6.2.1 Statistical analysis

Baseline characteristics will be summarised by randomised group. Patients failing to complete study drug will be listed, with accompanying reasons. The primary endpoint will be mean changes in log₁₀ d-dimer levels from baseline at weeks 8 and 12. The proportion of patients with d-dimer < 165 ng/mL will also be summarised.

Mean or median changes, or percentages, as appropriate, in primary and secondary endpoints will be plotted by study week.

Formal analyses will compare the randomised treatment arms in terms of mean differences in changes in log₁₀ d-dimer at week 8 and week 12 using repeated measures regression methods. Models will be fitted using maximum likelihood methods using robust standard errors. Simple unadjusted models will initially be used to estimate the difference between randomised treatment arms in mean changes in log₁₀ d-dimer. Models adjusted for key baseline covariates will also be fitted. If there is overall evidence of a difference between randomised treatment arms at $2p < 0.05$, then further sensitivity analyses will also be performed using simple two-sample (t-test or rank-sum test) applied to the mean change in log₁₀ d-dimer at weeks 8 and 12.

Similar longitudinal methods will also be used to analyse mean changes from baseline in, or proportions of, secondary endpoints at weeks 8 and 12.

Differences between randomised treatment arms in mean changes in, or proportions of, all endpoints at week 18 will be investigated using linear regression or logistic regression methods.

6.2.2 Safety analysis

The proportion of participants with all DAIDS (Division of AIDS) grade adverse events and DAIDS grade 3/4 adverse events (see Appendix 1) will be summarised by randomised treatment group, by severity and by relation to study drug for all subjects treated with study drug. Serious adverse events will be summarised for all enrolled subjects. The analysis of safety variables will be done according to a per protocol approach.

A particular focus of safety analyses will be bleeding events. These will be solicited adverse events, and classified according to Bleeding Academic Research Consortium (BARC) criteria¹⁶ (see Appendix 2) as BARC Type 1, 2, 3, 4 or 5 bleeding events. Bleeding events reported as unsolicited adverse events or serious adverse events will also be summarised. The proportions of patients with bleeding events will be compared between treatment arms using chi-square tests. If numbers of events are small, some bleeding events may be aggregated.

